7.1.2. Rechallenge

7.1.2.1. Study Drug Restart or Rechallenge After Liver Stopping Criteria Met

Study drug restart/rechallenge after liver chemistry stopping criteria are met is allowed in this study. If the subject meets liver chemistry stopping criteria, do not restart/rechallenge the subject with study drug unless:

- liver tests have returned to subject's baseline values
- sponsor medical monitor approval is granted
- ethics and/or IRB approval is obtained, if required

NOTE: If study drug was interrupted for suspected intervention-induced liver injury, the subject should be informed of the risk of death, liver transplantation, hospitalization, and jaundice before resumption of dosing.

Refer to [Section 10.5](#) for details on the restart/rechallenge process.

If sponsor medical monitor approval to restart/rechallenge the subject with study drug is **not granted**, then the subject must permanently discontinue study drug and may continue in the study for protocol-specified study assessments.

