7.1. Discontinuation of Study Drug

In rare instances, it may be necessary for a subject to permanently discontinue study drug. The reason for permanent discontinuation of study drug will be documented. If study drug is prematurely and permanently discontinued, the subject will be encouraged to remain in the study to be evaluated for safety and efficacy. Subjects should continue to complete study assessments as outlined in the SoA ([Section 1.3](#)) where possible, with the exception of study drug administration, and anti-drug antibody sample and PK sample collection. Reasons for removal from study drug include any of the following:

- subject request
- death
- lost to follow-up
- termination of study by sponsor
- emergency unblinding
- liver chemistry stopping criteria (see [Section 7.1.1](#))
- serious infections
- the subject becomes pregnant while on study drug
- malignancy
- subject develops CTCAE v5.0 grade 3 or higher SAE or AE(s) that is considered by the investigator to be related to study drug
- subject develops an illness that, in the opinion of the Investigator, would interfere with his or her continued participation, if the risk of continuing with study drug outweighs the potential benefit
- subject uses prohibited concomitant medications, as defined in [Section 6.8.3](#), that may present a risk to the safety of the subject in the opinion of the Investigator or the Medical Monitor
- subject is non-compliant with TB prophylaxis (if applicable) or develops active TB at any time during the study
- subject is significantly non-compliant with study procedures which would put the subject at risk for continued participation in the trial as determined by the Investigator or Medical Monitor
- subjects with disease progression or not responding to treatment are to be withdrawn from study drug treatment based on Investigator's discretion

- Starting at Week 24, subjects who have not met clinical Disease Activity for PsA (cDAPSA) low disease activity ($cDAPSA \leq 14$) at 2 consecutive visits (e.g. at Week 20 and Week 24) will be discontinued from study drug and can receive standard of care treatment as deemed appropriate by the Investigator.

Subjects with newly diagnosed IBD during the study must:

- discontinue study drug and be followed-up until resolution of active IBD symptoms
- be referred, as appropriate, to a health care professional treating IBD, such as a gastroenterologist

[figure not shown]

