7.1.1. Liver Chemistry Stopping Criteria

Discontinuation of study drug for abnormal liver tests is required by the investigator when a subject meets 1 of the conditions outlined in the algorithm or in the presence of abnormal liver chemistries not meeting protocol-specified stopping rules if the investigator believes that it is in the best interest of the subject ([Figure 2](#)). The investigator may consider rechallenge if a reasonable alternative explanation is identified, liver tests have returned to baseline levels, and after consultation with the medical monitor.

Figure 3. Phase 2 Liver Chemistry Stopping Criteria and Increased Monitoring Algorithm¹

Abbreviations: ALT = alanine transaminase; AST = aspartate transaminase; INR = international normalized ratio; SAE = serious adverse event; Tbili = total bilirubin; ULN = upper limit of normal. Note: INR will be collected only if ALT or AST $\geq 3 \times \text{ULN}$

¹ Liver Safety: Suggested actions and follow-up assessments can be found in Section 10.5.

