
MONITORING:
 
If ALT or AST $\geq 3 \times$ ULN AND total bilirubin $\geq 2 \times$ ULN or INR > 1.5:
 
 Repeat liver chemistry tests (include ALT, AST, alkaline phosphatase, total bilirubin, and INR) and perform liver event follow-up assessments within 24 hours. Monitor subject twice weekly until liver chemistry test abnormalities resolve, stabilize, or return to baseline. A hepatology consultation is recommended. 
If ALT or AST $\geq 3 \times$ ULN AND total bilirubin $< 2 \times$ ULN and INR ≤ 1.5:
 
 Repeat liver chemistry tests (include ALT, AST, alkaline phosphatase, total bilirubin, and INR) and perform liver chemistry follow-up assessments within 24 to 72 hours. Monitor subjects twice weekly until liver chemistry abnormalities resolve, stabilize, or return to baseline, or the study drug has been discontinued; then decrease monitoring to once weekly or less. Do not restart/rechallenge subject with study drug unless allowed per-protocol and sponsor approval is granted. 	
 Obtain complete blood count with differential to assess eosinophilia. Record the appearance or worsening of clinical symptoms of liver injury, or hypersensitivity, on the eCRF. Record use of concomitant medications (including acetaminophen, herbal remedies, and other over-the-counter medications) on the concomitant medications eCRF. Record alcohol use on the liver event alcohol intake form. 
If ALT or AST $\geq 3 \times$ ULN AND total bilirubin $\geq 2 \times$ ULN or INR > 1.5 obtain the following in addition to the assessments listed above:
 
 Antinuclear antibody, anti-smooth muscle antibody, type 1 anti-liver kidney microsomal antibodies, and quantitative total immunoglobulin G or gamma globulins. Serum acetaminophen adduct assay, when available, to assess potential acetaminophen contribution to liver injury in subjects with definite or likely acetaminophen use in the preceding week. Liver imaging (ultrasound, magnetic resonance, or computerized tomography) to evaluate liver disease. Liver biopsy may be considered and discussed with local specialist if available, for instance: 
 In subjects when serology raises the possibility of autoimmune hepatitis.
---	--

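### Protocol Sections 7.1.1 and 7.1.2.1 give different conditions for restarting study drug after a liver stopping criterion is met, and Section 10.5 does not settle which apply

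*Protocol*

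**What the plan says.** Four places in the protocol bear on restart after a liver event.

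- **Section 7.1** opens with a general sentence on permanence: "In rare instances, it may be necessary for a subject to permanently discontinue study drug". The list that follows gives reasons for removal from study drug. It includes the liver chemistry stopping criteria, with a cross-reference to Section 7.1.1.
- **Section 7.1.1** makes stopping mandatory: "Discontinuation of study drug for abnormal liver tests is required by the investigator when a subject meets 1 of the conditions outlined in the algorithm". On restart it gives the investigator a conditional permission: "may consider rechallenge if a reasonable alternative explanation is identified, liver tests have returned to baseline levels, and after consultation with the medical monitor".
- **Section 7.1.2.1** starts from a general permission: "Study drug restart/rechallenge after liver chemistry stopping criteria are met is allowed in this study". It goes on to say that the subject is not to be restarted unless three things hold. The first is that "liver tests have returned to subject's baseline values". The others are approval by the sponsor's medical monitor and, if required, approval by an ethics committee or IRB. A note adds: "If study drug was interrupted for suspected intervention-induced liver injury, the subject should be informed of the risk of death", followed by liver transplantation, hospitalization and jaundice, all to be explained before dosing resumes. If the monitor's approval is withheld, discontinuation is permanent. For the process, the reader is sent to Section 10.5.
- **Section 10.5** lists six stopping criteria and calls for immediate discontinuation, without saying whether this is temporary or permanent. Its one sentence on restart is: "Do not restart/rechallenge subject with study drug unless allowed per-protocol and sponsor approval is granted".

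**The concern.** A condition on cause appears in one section and is missing from the next, although both govern the same decision. The note in 7.1.2.1 makes the omission look more than accidental. It supplies disclosure wording for resuming treatment after an injury suspected to come from the study drug, which is the kind of case that the alternative-explanation condition in 7.1.1 would most often screen out. Section 10.5 is where the question should be settled, and it sends the reader back to the protocol.

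The decision at stake is whether to re-expose a subject after a possible drug-induced liver event. The trial gives weekly injections over a 51-week treatment period at approximately 100 sites. Section 7.1.2.1 excludes none of the six criteria in Section 10.5. It therefore also covers transaminase elevation combined with raised bilirubin or INR, which Section 10.5 itself flags as a possible sign of severe liver injury. Investigators and the medical monitor need one rule, and subjects need a risk disclosure that matches it.

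**Working it through.** No figure is involved, so no arithmetic applies. The check sets the restart conditions side by side and runs test cases through them.

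| Condition | 7.1.1 | 7.1.2.1 | 10.5 |
|---|---|---|---|
| Alternative explanation for the abnormality | Required | Not mentioned | Not mentioned |
| Liver tests back to baseline | Required | Required | Not stated as a restart condition |
| Medical monitor or sponsor | Consultation with the monitor | Approval by the monitor | Approval by the sponsor |
| Ethics committee or IRB | Not mentioned | Approval, if required | Not mentioned |
| Further reference | None on restart | To 10.5 for the process | Back to the protocol |

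**Case A.** A subject meets a liver stopping criterion and drug-induced injury is suspected. No alternative explanation is found. Liver tests return to baseline, the medical monitor approves, and ethics approval is given if required.

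1. Under 7.1.1 the first condition fails. The permission to consider rechallenge is not opened. This is by implication: the text grants a conditional permission and does not state a prohibition.
2. Under 7.1.2.1 every listed condition is met, restart is described as generally allowed, and the note addresses resumption after suspected drug-induced injury. The section can be read to allow restart.
3. Under 10.5 restart depends on the protocol allowing it and on sponsor approval. The second part is met. The first returns the reader to steps 1 and 2.
4. Under 7.1 the liver item points to 7.1.1, so it adds no independent answer.

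**Case B.** The same subject, but an alternative explanation is identified. The listed conditions of both 7.1.1 and 7.1.2.1 are now met and the sections agree.

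The difference in outcome therefore rests on one condition, the alternative explanation. It arises only when liver tests recover and no other cause is found.

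**Case A read cumulatively.** If the conditions of 7.1.1 and 7.1.2.1 are all applied together, Case A does not qualify. The answer for Case A thus depends on whether the reader combines the lists, and no sentence tells the reader to do so.

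Two further observations:

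- For the haematology and creatinine criteria, Section 7.1 separates interruption from permanent discontinuation and states what role an alternative cause plays. The liver text does not do this as clearly.
- Section 7.1.1 points to Figure 2, which is the modelling of PsA endpoints; the liver algorithm is Figure 3.

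**The case against.** The strongest reply is that the two lists are compatible. Section 7.1.2.1 is worded as a prohibition with exceptions, which states necessary conditions and does not say that they suffice. A site can apply all of them together with the alternative explanation from 7.1.1. On that reading the note covers drug stopped on suspicion, where another cause is found later. This stands as a possible reading. Against it, no sentence says that the lists are cumulative, and a warning of death and liver transplantation fits poorly with an injury already attributed to something else. That last point is a judgement about fit, not proof.

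A reader might infer more than the documents support, in four ways:

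- **That one section forbids what another permits.** Section 7.1.1 contains no prohibition. Its bar on Case A is only implied.
- **That Section 7.1 makes every liver stop permanent.** Its opening sentence is general, its liver item leads to 7.1.1, where rechallenge is provided for, and 7.1.2.1 says that discontinuation becomes permanent when the monitor's approval is not granted.
- **That consultation and approval conflict.** They can both be satisfied: consult before considering rechallenge, obtain approval before restarting. The terms differ, but not irreconcilably.
- **That sites could freely reach opposite decisions, even in the most serious cases.** Section 7.1.2.1 requires the medical monitor's approval and Section 10.5 requires the sponsor's, so on those sections no site restarts alone. Section 7.1 also lists, as a separate reason for removal, a grade 3 or higher event judged related to study drug, with no reference to rechallenge. That limits the worst case, though it depends on the grade and on the investigator's judgement of relatedness.

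Finally, Figure 3 is not available in the text reviewed and may carry further wording. Nothing is inferred from it either way.

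**Conclusion.** The point holds as an unresolved inconsistency in a safety rule. Sections 7.1.1 and 7.1.2.1 state different restart conditions, the difference changes the answer for a definable subject, and the section cited for the process does not resolve it. Central approval reduces the practical effect but does not remove the ambiguity, because 7.1.2.1 gives the medical monitor no criterion on cause to apply.

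It does not hold as a flat contradiction in which a subject is expressly excluded from rechallenge in one place and admitted in another. The documents support only an implied bar, set against a permission that can be read with or without it.

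The subjects affected are those who meet one of the six criteria in Section 10.5, recover to baseline and have no alternative explanation. The documents give no incidence, so no count or range is offered. Sample size, power and alpha are unaffected. The conclusion rests on the visible text and assumes that Figure 3 does not reconcile the sections. It takes no view on which restart conditions are right.

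**What to change.** Reconcile Protocol Sections 7.1, 7.1.1, 7.1.2.1 and 10.5 into one list of restart conditions, stated once and cross-referenced from the other places. The list should:

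- state whether an alternative explanation is required;
- describe the medical monitor's role in the same terms throughout;
- say when a liver stop is an interruption and when it is permanent;
- be matched by the note in 7.1.2.1, so that the risk disclosure fits the cases in which restart is open.

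The pointer to Section 10.5 should lead to an actual process or be removed, and the figure reference in 7.1.1 should be corrected. The sponsor's medical team decides which conditions apply.

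The cost is a protocol wording amendment with its usual approvals. No new procedures, visits or subjects are needed.

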7.2. Subject Discontinuation/Withdrawal from the Study

Reasons for removal of a subject from the study are:

- termination of study by sponsor
- death
- withdrawal of consent from study
- lost to follow-up

Withdrawal of consent from study:

- A subject may withdraw from the study at any time without jeopardizing subsequent medical care.
- At the time of discontinuing from the study, if possible, an End of Treatment visit should be conducted, as shown in the SoA. See SoA ([Section 1.3](#)) for data to be collected at the time of study discontinuation and follow-up and for any further evaluations that need to be completed. See [Section 7.1 for procedures if the study drug is prematurely discontinued and does not withdraw from the study](#).
- The subject will be permanently discontinued from the study drug and the study at that time.
- If the subject withdraws consent for disclosure of future information, the sponsor may retain and continue to use any data collected before such a withdrawal of consent.
- If a subject withdraws from the study, he/she may request destruction of any samples taken and not tested, and the investigator must document this in the site study records and notify the sponsor or its designee.

7.3. Lost to Follow-up

A subject will be considered lost to follow-up if he or she repeatedly fails to return for scheduled visits and is unable to be contacted by the study site.

The following actions must be taken if a subject fails to return to the clinic for a required study visit:

- The site must attempt to contact the subject and reschedule the missed visit as soon as possible, counsel the subject on the importance of maintaining the assigned visit schedule and ascertain whether the subject wishes to and/or should continue in the study.
- Before a subject is deemed lost to follow-up, the investigator or designee must make every effort to regain contact with the subject (where possible, 3 attempts at known

effective points of contact [eg, phone, e-mail, text], and if necessary, a certified letter to the subject's last known mailing address or local equivalent methods). These contact attempts should be documented in the subject's medical record.

- Should the subject continue to be unreachable, he/she will be considered lost to follow-up.

8. Study Assessments and Procedures

- Informed consent must be obtained before any study-related procedures are performed. In regions where the legal age of consent is older than 18 years, informed consent must be obtained from and signed by the subject.
- Study procedures and their timing are summarized in the SoA ([Section 1.3](#)). Protocol waivers or exemptions are not allowed.
- Day 1 corresponds to the date of the first dose of study drug.
- Visit/dosing windows of ± 3 days on either side of the scheduled visits/dosing are permitted. In case of a delayed or missed dose, the investigator should return subjects on the original visit/dosing schedule in relation to Day 1 for subsequent doses. The window of ± 3 days is relative to Day 1 and applicable for all subsequent visits/dosing. The minimum time between doses should be no less than 4 days and no more than 10 days.
- All assessments are to be completed before study drug administration, unless otherwise specified. It is recommended that patient-reported outcome assessments be completed first. X-rays required at Week 16 and at the End of Treatment visit may be completed ± 3 days of dosing.
- Immediate safety concerns should be discussed with the sponsor immediately upon occurrence or awareness to determine if the subject should continue or discontinue study drug.
- Adherence to the study design requirements, including those specified in the SoA ([Section 1.3](#)), is essential and required for study conduct.
- All screening evaluations must be completed and reviewed to confirm that potential subjects meet all eligibility criteria. The investigator will maintain a screening log to record details of all subjects screened and to confirm eligibility or record reasons for screening failure, as applicable.
- Procedures conducted as part of the subject's routine clinical management (eg, chest x-rays) and obtained before signing of the ICF may be utilized for screening or baseline purposes provided the procedures met the protocol-specified criteria and were performed within the timeframe defined in the SoA ([Section 1.3](#)).
- Repeat or unscheduled samples may be taken for safety reasons or for technical issues with the samples.

8.1. Efficacy Assessments

Planned timepoints for all efficacy assessments are provided in the SoA ([Section 1.3](#)). The study site should make every attempt to have the same investigator conduct efficacy assessments throughout the study for each subject.

8.1.1. Composite Measures

The calculation of the composite scores will be performed by the sponsor or designee based on the assessments entered by the study investigator(s) on the appropriate eCRFs.

8.1.1.1. American College of Rheumatology Response Criteria

The ACR criteria are standard criteria to measure the effectiveness of various arthritis medications or treatments in clinical trials. The ACR criteria were developed for rheumatoid arthritis but now are also frequently used for primary outcome measure in PsA clinical trials ([American College of Rheumatology, 2019](#)).

The ACR criteria are reported as percentage (%) improvement, comparing disease activity at 2 discrete timepoints (baseline and postbaseline comparison). The ACR criteria are indicated as:

- ACR20 is $\geq 20\%$ improvement
- ACR50 is $\geq 50\%$ improvement; ACR50 responders include ACR20 responders
- ACR 70% (ACR70) is $\geq 70\%$ improvement; ACR70 responders include ACR20 and ACR50 responders

The ACR20 criteria require that the subject experiences an improvement in the following parameters compared to baseline:

- $\geq 20\%$ reduction in TJC68 (see [Section 8.1.3.1](#))
- $\geq 20\%$ reduction in SJC66 (see [Section 8.1.3.1](#))
- $\geq 20\%$ reduction in 3 of 5 additional measures:
 - Subject's Assessment of Pain (see [Section 8.1.2.3](#))
 - Subject's Global Assessment of Disease Activity (see [Section 8.1.2.2](#))
 - Investigator's Global Assessment of Disease Activity (see [Section 8.1.3.2](#))
 - HAQ-DI (see [Section 8.1.2.6](#))
 - Acute phase reactant (C-reactive protein [CRP]).

Analyses of ACR50 and ACR70 include the same criteria as ACR20, with the use of a higher percentage improvement (50% and 70%, respectively) instead of 20% ([European Medicines Agency, 2007](#)).

The proportion of subjects achieving ACR20, ACR50, and ACR70 will be evaluated at Week 16.

8.1.1.2. Disease Activity Score in 28 Joints

The Disease Activity Score in 28 joints (DAS28)-CRP was developed to measure disease activity in subjects with rheumatoid arthritis. It is a composite score derived from the following measures ([Mease, 2011](#)):

- 28 tender joint count (see [Section 8.1.3.1](#))
- 28 swollen joint count (see [Section 8.1.3.1](#))

- CRP
- Subject's Global Health Assessment (corresponds to Subject's Global Assessment of Disease Activity, see [Section 8.1.2.2](#)).

Generally, remission is considered achieved if the score is between 0 and < 2.6 . Low activity corresponds to 2.6 to < 3.2 . Moderate activity is between 3.2 and ≤ 5.1 , while high activity is strictly above 5.1.

Change in DAS28-CRP composite score will be evaluated at Week 16.

8.1.1.3. Disease Activity in Psoriatic Arthritis

The Disease Activity in Psoriatic Arthritis (DAPSA) is a composite score calculated by summing the following variables ([Mease, 2011](#)):

- 68 tender joint count (see [Section 8.1.3.1](#))
- 66 swollen joint count (see [Section 8.1.3.1](#))
- Subject's Assessment of Pain (see [Section 8.1.2.3](#))
- Subject's Global Assessment of Disease Activity (see [Section 8.1.2.2](#))
- CRP level in mg/dL.

Change in DAPSA and clinical DAPSA (cDAPSA; sum of the above variables, but omitting CRP) composite scores will be evaluated at Week 16.

Proportion achieving DAPSA and cDAPSA low disease activity (DAPSA/cDAPSA ≤ 14) and remission (DAPSA/cDAPSA ≤ 4) will be evaluated starting at Week 16.

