8.1.1.5. Minimal Disease Activity and Very Low Disease Activity

The criteria for MDA were developed for rheumatoid arthritis, but a PsA-specific definition of MDA has been constructed (Coates et al, 2010). These criteria were validated and are now considered as a step towards “treatment to target” in PsA, ie, the goal of achieving remission or low disease activity state (Coates et al, 2010; Mease, 2011).

A subject is classified as in MDA when 5 of the following 7 criteria are met (Mease, 2011):

- 68 tender joint count ≤ 1 (see [Section 8.1.3.1](#))
- 66 swollen joint count ≤ 1 (see [Section 8.1.3.1](#))
- PASI ≤ 1 or BSA $\leq 3\%$ (see [Section 8.1.3.3](#))
- Subject’s Pain Assessment (visual analogue scale [VAS]) ≤ 15 mm (see [Section 8.1.2.3](#))
- Subject’s Global Activity VAS ≤ 20 mm (corresponds to Subject’s Global Assessment of Disease Activity, see [Section 8.1.2.2](#))
- HAQ-DI ≤ 0.5 (see [Section 8.1.2.6](#))
- Tender enthesal points ≤ 1 site out of 6 sites included in LEI (see [Section 8.1.3.5](#)).

A subject is classified as in very low disease activity (VLDA) when all 7 criteria described above are met.

The proportion of subjects achieving MDA and VLDA will be evaluated at Week 16.

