8.1.2.3. Subject’s Assessment of Pain (VAS)

Pain will be assessed by the subject at the designated study visits listed in SoA ([Section 1.3](#)) using a VAS.

The VAS is a horizontal line, 100 mm in length, with anchor statements on the left (0 mm) and on the right (100 mm). The subject will be asked to place a single vertical line through the VAS at the point that best corresponds to their feeling of pain.

The score is obtained by measuring the distance from 0 to the line drawn by the subject.

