**Appendix 2.5 Disease Activity index for Psoriatic Arthritis (DAPSA)**

DAPSA is the numerical sum of 66 swollen and 68 tender joint counts, pain, SGADA (pain and SGADA scored on a 0–10 scale) and CRP (mg/dL))

DAPSA = TJC68 + SJC66 + SGADA/10 + SAPVAS/10 + CRP;

where TJC=tender joint count and SJC=swollen joint count;

ln = natural logarithm;

SGADA = subject's global assessment of disease activity on a 0-100 VAS;

SAPVAS = subject's global assessment of pain on a 0-100 VAS;

CRP = C-reactive protein measured in mg/dL.

The cDAPSA, which was derived from the DAPSA, includes all DAPSA components but excludes CRP to obtain a fully clinical score.

A DAPSA, cDAPSA score of  $\leq 14$  represents low disease activity, and a score of  $\leq 4$  represents remission.

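### The protocol and the SAP scale the two VAS terms of cDAPSA differently under the same cut-offs, and neither says which formula drives the mandatory study-drug stop

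*Protocol*

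**What the plan says.** **Protocol.** Section 8.1.1.3 says: "The Disease Activity in Psoriatic Arthritis (DAPSA) is a composite score calculated by summing the following variables". The list that follows is TJC68, SJC66, pain, subject global assessment and CRP. cDAPSA is the "sum of the above variables, but omitting CRP". The section sends the reader to 8.1.2.2 and 8.1.2.3 for the global and pain items. Both sections use a 100 mm line, and in both "The score is obtained by measuring the distance from 0 to the line drawn by the subject". Nothing in the protocol divides these scores by 10. Section 8.1.1.5 uses the same two items in millimetres, for example "Pain Assessment (visual analogue scale [VAS]) ≤ 15 mm".

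**SAP.** Appendix 2.5 gives "DAPSA = TJC68 + SJC66 + SGADA/10 + SAPVAS/10 + CRP" and says that cDAPSA "includes all DAPSA components but excludes CRP to obtain a fully clinical score".

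**Shared cut-offs.** Both documents take 14 or less as low disease activity and 4 or less as remission.

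**The stop.** From Week 24, a subject who misses the cut-off of 14 at two consecutive visits "will be discontinued from study drug and can receive standard of care treatment as deemed appropriate by the Investigator" (Protocol 7.1; also 4.1 and footnote c of the Schedule of Activities). SAP 2.1 repeats the rule. Protocol 8.1.1 assigns calculation of composite scores to the sponsor or its designee and names no formula.

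**The concern.** One cut-off is applied to two scores that differ by up to 180 points. For a table of exploratory endpoints this would be a matter of clarification. Here the score also decides whether a subject stays on drug, so the scaling should not be left to be inferred.

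If the two formulas were used for different purposes, a subject could be counted as in SAP low disease activity, or even SAP remission, while meeting the condition for a required stop. Four things depend on the answer:

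- study-drug exposure from Week 24;
- the disposition row for subjects who did not meet cDAPSA low disease activity (SAP 6.2);
- the Period 2 compliance denominator, which allows for withdrawal under this rule (SAP 6.5);
- exploratory results after the stop, because stopped subjects may receive standard of care while their assessments continue.

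**Working it through.** The documents give no worked cDAPSA value to reproduce, so the check applies each formula as written.

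**Inputs.** T = TJC68 (0 to 68) and S = SJC66 (0 to 66). P = pain and G = subject global, each 0 to 100 mm (Protocol 8.1.2.3 and 8.1.2.2). The cut-offs are 14 and 4 (Protocol 8.1.1.3; SAP Appendix 2.5). The VLDA limits are T ≤ 1, S ≤ 1, P ≤ 15 mm and G ≤ 20 mm (Protocol 8.1.1.5). The other three VLDA criteria (skin, HAQ-DI, entheseal points) do not enter cDAPSA, so a subject at these four limits can meet all seven.

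**Formulas.**

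- Protocol: T + S + P + G
- SAP: T + S + P/10 + G/10
- Difference: 0.9 × (P + G), which is never negative and is at most 0.9 × 200 = 180

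**Range.** Protocol maximum: 68 + 66 + 100 + 100 = 334. SAP maximum: 68 + 66 + 10 + 10 = 154.

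**Worked cases.**

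| T | S | P (mm) | G (mm) | Protocol | SAP | SAP status | Protocol above 14? |
|---|---|---|---|---|---|---|---|
| 1 | 1 | 15 | 20 | 37 | 5.5 | low disease activity | yes |
| 0 | 0 | 15 | 20 | 35 | 3.5 | remission | yes |
| 1 | 1 | 10 | 10 | 22 | 4.0 | remission | yes |
| 0 | 0 | 10 | 10 | 20 | 2.0 | remission | yes |
| 1 | 1 | 5 | 7 | 14 | 3.2 | remission | no |
| 0 | 0 | 5 | 5 | 10 | 1.0 | remission | no |

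All six cases lie within the four VLDA limits that cDAPSA shares, yet four exceed 14 by the protocol sum.

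**No affected joints.** The protocol sum is 14 or less only if P + G ≤ 14 mm out of 200 mm. SAP remission needs P + G ≤ 40 mm. Any total from 15 to 40 mm is therefore SAP remission with a protocol score above 14. The VLDA limits allow P + G up to 15 + 20 = 35 mm.

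**All combinations of whole joint counts and whole millimetres.**

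- SAP score 4 or less: 1,943 of 2,815 combinations (69%) exceed 14 by the protocol sum.
- SAP score 14 or less: 210,260 of 213,320 combinations (98.6%) do so.
- The reverse (protocol 14 or less, SAP above 14) cannot occur, because the difference is never negative.

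These are shares of possible score combinations, not of patients.

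**Timing.** The stop starts at Week 24. The primary endpoint and all secondary efficacy endpoints in the testing sequence are at Week 16 (Protocol 9.1.1; SAP 6.6), so neither those tests nor the power statements depend on it.

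**The case against.** The best reply is that the protocol left out a detail and did not set a rival formula. Its composite sections are mainly component lists: DAS28-CRP appears without its equation, and PASDAS is called weighted without weights. SAP Appendix 2 supplies the scoring. Section 8.1.1.3 also cites a published source, not available here, that may fix the scaling. The literal sum fits poorly with the protocol's own VLDA limits. Since the sponsor or designee computes the composites, one calculation with the SAP formula may have served every purpose.

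Much of this stands. A reader might infer that the stop follows the protocol formula while the endpoint tables follow the SAP, so that the disposition row and the tables must disagree. No passage says so. A reader might also infer that responders were taken off drug and every Week 52 result is distorted. That would require the literal sum to have been used at both visits, and the documents do not show that it was. Stopped subjects continue assessments, and efficacy results after Week 16 are exploratory and reported without p-values (SAP 6.6.5).

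The reply does not remove the contradiction. Section 8.1.1.3 does state an operation, a sum, and points to items scored in millimetres. Neither Section 7.1 nor footnote c refers to the SAP formula. VAS scaling was already a practical issue in this trial: SAP 6.6.1 and 6.6.2 deal with lines not 100 mm long, spoken or written numbers, and data on a 0 to 10 scale.

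**Conclusion.** This is a cross-document inconsistency, wrong as written. The two formulas differ by 0.9 times the sum of the two VAS scores, and a required study-drug stop depends on the result without either document saying which formula applies.

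The consequence is conditional. If the literal sum were applied at two consecutive visits from Week 24, some subjects within the VLDA limits would have to stop drug: 37 against 5.5 at those limits, and 20 against 2 with no affected joints and 10 mm on each scale. Not every VLDA subject would be caught, as the last two rows of the table show. A single visit above 14 is not a stop. The cut-off for the stop and for low disease activity is 14; remission is the separate cut-off of 4.

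The documents give no figure for how many subjects might be affected. The reach is limited to exposure from Week 24, disposition, Period 2 compliance and exploratory results after the stop. Which scaling should govern the stop is not decided here; the passages must be reconciled.

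**What to change.** 1. Reconcile Protocol 8.1.1.3 with SAP Appendix 2.5: print one explicit DAPSA and cDAPSA formula, identical in both, with the scaling of the pain and global terms shown.
2. State that this formula drives the Section 7.1 rule, the SAP 6.2 disposition row and the DAPSA/cDAPSA endpoints.
3. Establish which scaling was used for discontinuations already made under the rule. Run a programmed check, at both qualifying visits, that lists any such subject whose status differs between the two formulas.

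The cost is one formula line in a protocol clarification, a cross-reference in the SAP and a short program on data already collected. No new data are needed.
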